5.7 Interim Analyses

No formal interim analysis is planned for this study.

An independent DMC will review safety and efficacy data at regular intervals during the study. Further details can be found in Protocol Section 9.5 and the DMC charter and will not be covered in this SAP.

5.8 PRO Analysis

All PROs analyzed in this study will be assessed using the mean change from baseline as well as by participants achieving of a meaningful score difference at the Cycle 13 visit.

Document: S:\Q_146\Q_03974\MEK-NF-201\Prog_Stat\Documentation\SAP\MEK-NF-201 SAP v1.0.0.docx

Author:

Cycle 13 has been selected as the timepoint that will best allow the treatment effect to be captured in PRO scores. It is projected that a strong majority of participants who present a response will do so at or before Cycle 13, with the median time of response expected to be Cycle 5 to Cycle 9, so any associated pain or QoL improvements should be captured at the Cycle 13 visit. Choosing a later cycle would capture few additional responses and may be susceptible to increased amounts of missing data.

An addendum meaningful change threshold (MCT) SAP will provide detailed descriptions of the statistical methods, data derivations, and data displays for the meaningful change analyses of the clinical outcome assessment (COA) data collected in the MEK-NF-201 study. This addendum (PRO Addendum) for the meaningful change threshold analysis plan (MCTAP) is based on the MEK-NF-201 Protocol Amendment 4 dated 17 May 2022.

Statistical Analyses

6.1 Participant Disposition

Participant disposition information, as listed in Section 4.3.1, will be summarized separately for each age cohort by absolute counts (n) and percentages (%) for the Enrolled Set. Percentages will be based on the number of participants with data in the relevant age cohort.

All disposition data will also be listed.

6.2 Protocol Deviations

All protocol deviations that are categorized as defined in Section 4.3.2, will be summarized by the number of participants (n) and percentages (%) for the FAS. Percentages will be based on the number of participants with data in the relevant age cohort.

6.3 Demographics

Baseline demographics data as laid out in Section 4.3.3 include continuous and categorical variables, which will be summarized as described in Section 5.1.2. Percentages will be based on the number of participants with data. These summaries will be presented for the FAS and PPS.

All demographic data will be listed, with a separate listing for changes in childbearing potential during the study.

6.4 Baseline Disease Characteristics

Baseline disease characteristics, as listed in Section 4.3.4.1, comprise continuous and categorical variables, which will be summarized as described in Section 5.1.2. Percentages will be based on the number of participants with data. These summaries will be presented for the FAS and PPS.

All baseline disease characteristics data will be listed.

6.5 Medical History

Medical history will be summarized by absolute counts (n) and percentages (%) for the FAS. All medical history records will be presented by SOC and PT as laid out in Section 4.3.5.1.

Document: S:\Q_146\Q_03974\MEK-NF-201\Prog_Stat\Documentation\SAP\MEK-NF-201 SAP v1.0.0.docx

Author:

Additional summaries will be presented for absolute counts (n) and percentages (%) of participants who have prior PN or cancer related radiotherapy, surgery, or procedures.

All medical history data will be listed.

6.6 Concomitant Medication

Number of participants with at least one recorded concomitant medication, 4th level ATC codes and preferred terms will be summarized by absolute counts (n) and percentages (%) for the FAS. Percentages will be calculated based on the number of participants at risk for the specific age cohort. This summary will be presented for the Treatment Phase and the LTFU Phase.

All concomitant medication data will be listed.

6.7 Concomitant Surgeries and Procedures

Surgeries and procedures will be summarized by absolute counts (n) and percentages (%) for the FAS. Unless specified otherwise, results will be sorted alphabetically by SOC, and by decreasing frequency of participants presenting PTs within a SOC. In the event of PTs having equal frequencies, the PTs will be sorted alphabetically within the SOC. This summary will be presented by Treatment Phase and for the LTFU Phase.

All concomitant surgeries and procedures data will be listed.

6.8 Treatment Compliance

All treatment compliance data including tablets dispensed/returned and recorded instances of non-compliant dosing will be listed.

6.9 Exposure to Study Treatment

Exposure to study treatment will be summarized by the parameters listed in Section 4.3.7, as described in Section 5.1.2. Percentages will be based on the number of participants with data.

6.10 PRO Compliance & Completion

Compliance and completion rates will be provided for the PRO instruments corresponding to the secondary endpoints of PedsQL, NRS-11, and PII.

Compliance rate is calculated as participants with minimum requirements for scoring divided by the number of participants with PRO assessments expected. For compliance rates, the summaries will include reasons for missing observations among patients who were expected to complete the questionnaire by assessment.

For completion rate, this will be derived in a similar manner as the compliance rate, however the subset of the FAS who are considered eligible to complete each questionnaire, as per Table 14, is used as a fixed denominator. For completion rates, the summaries will include reasons for missing observations among the eligible participants within the eligible FAS population by assessment. Reasons for missing observations include, but are not limited to, progression, adverse event, subject withdrawal, lost to follow-up, patient or physician decision, patient was too ill to complete, not completed due to site staff error, technical problems with eDiary, patient non-compliance, etc.

Document: S:\Q_146\Q_03974\MEK-NF-201\Prog_Stat\Documentation\SAP\MEK-NF-201 SAP v1.0.0.docx

Author:

Table 14: PRO Age Range Eligibility

PROs	Ped	dsQL	NRS-11		PII
Age of Participant (years)	Self-report	Parent Proxy	Self-Report	Self-report	Parent Proxy
2		Х			
3		Х			
4		Х			
5	Х	Х			
6	Х	Х		Х	Х
7	Х	Х		Х	Х
8-17	Х	Х	Х	Х	Х
≥18	Х	Ха	Х	Х	

a If a participant is ≥ 18 years of age, but in the opinion of the investigator has cognitive deficiencies that would inhibit accurate collection of PRO data, a parent or legal guardian must also complete the appropriate parent-proxy PRO.

For the diary instruments where more than one day was expected (NRS-11 and PII), the number and percent of participants with ≥1 complete diary day, ≥2 complete diary days, ≥3 complete diary days, etc. for the diary periods associated with the study visits will also be provided.

All summaries of compliance/completion will be displayed with the relevant PROs.

6.11 Efficacy Analyses

The efficacy endpoints will include collected and derived continuous and categorical variables and will be summarized as described in Section 5.1.2, unless otherwise specified.

The FAS will be the primary analysis set of interest in all efficacy analyses, unless otherwise specified.

6.11.1 Primary Efficacy Analysis

To assess the primary efficacy endpoint, confirmed ORR by the end of the Treatment Phase as assessed by BICR will be presented as a percentage alongside the corresponding 2-sided 95% Clopper-Pearson Cl and the p-value from a one-sample two-sided binomial test for the confirmed ORR compared to the minimum clinically relevant response rates defined in Section 5.2. The overall assessment of the endpoint will be based on the exclusion of the minimum clinically relevant response rate by the lower tail of the 95% Cl.

Document: S:\Q_146\Q_03974\MEK-NF-201\Prog_Stat\Documentation\SAP\MEK-NF-201 SAP v1.0.0.docx

Author:

All tumor data from MRI assessments will be listed across both the Treatment and LTFU Phases.

6.11.1.1 Sensitivity Analysis of Primary Efficacy Analysis

A sensitivity analysis will be performed that mirrors the primary efficacy analysis but uses the PPS rather than the FAS.

As additional sensitivity analyses, the confirmed ORR will be summarized by each central BICR reader separately for both the FAS and the PPS.

6.11.2 Secondary Efficacy Analyses

6.11.2.1 Duration of response for participants whose best response is CR or PR using centrally read MRI volumetric analysis

DoR will be analyzed using Kaplan-Meier (KM) methods, with the median, lower, and upper quartile estimates of DoR and the corresponding 95% Cls (using the Brookmeyer and Crowley method). The number of participants with events (i.e., radiographic disease progression or death) or who are censored, as well as reason for censoring, will be presented separately by age cohort. "NE" will be presented where estimates of such were not estimable. Additionally, KM plots will be presented separately for each age cohort and will contain the number of participants at risk and the event rate. In addition, KM estimates with 95% Cls (using the log-log transformation) will also be presented at key timepoints such as 8, 12, 16, 20, and 24 months.

Censoring rules and the definition of confirmed response are laid out in Section 4.1.2.1.

The sensitivity analyses using REiNS criteria as outlined in Section 4.1.2.1.1 will also be summarized using the same method as described above.

In addition, a swimmer plot will be used to present duration of treatment (in days) where radiographic progression, first onset and confirmation of confirmed response, whether still on study at cutoff and death are displayed, split by cohort.

6.11.2.2 Change from Baseline in quality of life assessed by the age specific Pediatric Quality of Life Inventory

All PedsQL records will be listed by participant, visit and questionnaire type (self-report/parent proxy).

Actual values and change from baseline for each score listed in Section 4.1.2.2.1 will be summarized for each age cohort by visit, for participants overall and by confirmed objective response status (as defined with confirmed response rate in Section 4.1.1 using adjudicated values where appropriate) with self-report and parent proxy scores presented separately. The summaries presented will be number and percentage of participants with a non-missing score, mean, SD, median, minimum, and maximum values.

For PedsQL, a within-patient meaningful score change, or meaningful score difference (FDA, 2023), will be derived by anchor-based analysis of the study's data, as described in the meaningful change threshold analysis plan (Version 1.0, dated 12Sep2023). The primary focus of this will be on if a relevant difference exists at Cycle 13.

Document: S:\Q_146\Q_03974\MEK-NF-201\Prog_Stat\Documentation\SAP\MEK-NF-201 SAP v1.0.0.docx
Author:

Statistical Analysis Plan SpringWorks Therapeutics Protocol Number: MEK-NF-201

In addition to the anchor-based estimates described above, the number and percentage of participants with a within-patient meaningful score change estimates are defined below and will be considered as a supportive analysis. For PedsQL Scale Scores, the meaningful score difference will be defined separately for adult, pediatric self-report, and pediatric parent proxy data. In each case, it will be defined as 0.5*SD, where SD is calculated from the baseline Scale Score data. This is in-line with the difference used on the selumetinib SPRINT study (Gross, 2018) and serves as the lower bound for minimally detectable change (Norman, 2003).

The number and percentage of participants with a change representing a clinically meaningful improvement (alongside associated 95% Clopper-Pearson Cls) will be presented for both thresholds.

In addition, within each age cohort, the proportion of participants reaching the anchor-based and distribution threshold will be analyzed in the subgroup of participants who have a confirmed objective response status versus the subgroup of those who do not. This is to further characterize the relationship between PRO improvement and the clinical endpoint of tumor response. The proportion of participants reaching the anchor-based (and distribution) thresholds will be summarized with 95% Clopper-Pearson Cls by confirmed objective response status, and the differences in the proportions of participants reaching the anchor-based/distribution thresholds between responders and non-responders will be tested using a Chi-Square test at a 5% significance level.

An MMRM will be fitted separately by age cohort and questionnaire type for each PedsQL score listed in Section 4.1.2.2.1. Change from baseline in PedsQL score will be the dependent variable, visit will be fitted as a fixed effect, and baseline PedsQL score used as a covariate. Covariance structures will be trialed in the order of decreasing complexity, with the first structure that converges without error used. The structures tested are as follows: Unstructured, Heterogenous Toeplitz, Heterogenous Autoregressive, Autoregressive, Heterogenous Compound Symmetry, Compound Symmetry, Variance Components. A Kenward-Roger approximation will be used for the degrees of freedom. This model will be fitted twice, once using only data through Cycle 13, and once including data from the entire study (timepoints with < 5 subjects will not be presented). EOT and unscheduled visits will be mapped to the closest scheduled tumor visit following the rules outlined in Table 13, and will only be included in the model if the participant has no other record at that timepoint. For the MMRM change from baseline tables, the least square (LS) Means estimates will be presented with associated standard errors, 95% Cls and p-values by visit. Plots of the LS Means estimates over time with associated 95% Cl bands will be presented separately by age cohort and questionnaire type for both models.

Box and whiskers plots of change from baseline in total score will be presented by visit and confirmed objective response status for the adult cohort, pediatric cohort self-report, and pediatric cohort parent proxy separately.

A waterfall plot of change from baseline will be presented by visit for adult cohort, pediatric cohort self-report and pediatric cohort parent proxy separately for each PedsQL domain at Cycles 5 and 13 with a line representing the respective within-patient meaningful change threshold derived by anchor-based analysis. This plot will be color-coded by confirmed objective response status.

Additionally, a sensitivity analysis will be performed for each PedsQL score using the imputed data described in Section 5.5.1.1. The MMRM analysis described above will be performed with data up to Cycle 13. LS Means estimates, associated standard errors, 95% Cls and p-values will be presented by visit.

Document: S:\Q_146\Q_03974\MEK-NF-201\Prog_Stat\Documentation\SAP\MEK-NF-201 SAP v1.0.0.docx

Author:

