Tumor volume (mL) will be assessed using MRI scans that will be taken at screening, then every 4 cycles at Cycles 5, 9, 13, 17, 21, 24, and ET for the Treatment Phase, and Cycle 28 and every 4 cycles after that, up to and including end of treatment (EOT), for the LTFU Phase, if applicable. Only tumor assessments during the Treatment Phase and prior to the first treatment start date in the long-term follow up will be considered for the determination of confirmed response. Unscheduled visits will be mapped to a visit window based on the criteria in Section 5.6.

The FAS will be used to calculate the confirmed ORR. Participants who do not have a post-baseline MRI assessment or do not achieve a confirmed response will be categorized as non-responders, and their best overall response will be deemed as "Missing".

Document: S:\Q_146\Q_03974\MEK-NF-201\Prog_Stat\Documentation\SAP\MEK-NF-201 SAP v1.0.0.docx

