5.1.2 Default Descriptive Statistics and Data Rules

Unless otherwise stated, summary statistics including the number of participants, mean, standard deviation (SD), median, minimum, and maximum, will be presented by age cohort for all continuous variables. Minimum and maximum values will be presented to the same decimal

Document: S:\Q_146\Q_03974\MEK-NF-201\Prog_Stat\Documentation\SAP\MEK-NF-201 SAP v1.0.0.docx

Author:

Protocol Number: MEK-NF-201

precision as the raw values, the mean and median values to one more, and the standard deviation, to two more decimal places than the raw values.

For categorical variables, per category, the absolute counts (n) and percentages (%) of participants in each with data, and if appropriate, the number of participants with missing data, will be presented for each age cohort. All percentages will be presented to one decimal place.

For AEs reported on a per-participant basis, medical history and concomitant medications, the denominator for the percentage calculation will be the number of participants in each age cohort. A participant will be considered at risk if the participant is in the Safety Analysis Set/FAS and entered the respective study period.

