5.5 Handling of Missing Data

Missing data will only be imputed in the following cases:

Document: S:\Q_146\Q_03974\MEK-NF-201\Prog_Stat\Documentation\SAP\MEK-NF-201 SAP v1.0.0.docx

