5.5.1 Secondary Efficacy Endpoints

5.5.1.1 Change from Baseline in QoL assessed by the age specific PedsQL

If ≤ 50% of questions in a given scale are missing, then the scale score will be imputed as the mean of the non-missing questions. If > 50% of questions are missing, then the scale score should not be calculated for that scale. The main analysis for this endpoint will be a mixed model for repeated measures (MMRM), which treats all missing data as missing at random (MAR).

A sensitivity analysis will be performed to assess the potential impact of this assumption if some data is missing not at random (MNAR). For this purpose, monotone and non-monotone missing values will be treated differently. Non-monotone missing values are values missing intermittently, where a participant may miss some PRO assessments but has PRO assessments for the same score later in the study. Monotone missing values are such that once a value is missing for a given score, no subsequent values for this score are available. Any given participant may have a combination of non-monotone and monotone missing values.

Non-monotone missing values are assumed to be MAR so will not be directly imputed as the analysis by MMRM already makes this assumption. Monotone data, however, will be considered MNAR and imputed to be equal to the participant's baseline score. This choice of imputation represents a negative outcome of no improvement in QoL for each participant.

The details of the sensitivity analysis to be performed with this imputed data are given in Section 6.11.2.2.

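### The SAP sets no denominator or missing-data rule for the Cycle 13 meaningful-improvement rates (PedsQL, NRS-11, PII), and its default implies an observed-case rate

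*SAP*

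**What the plan says.** SAP 2.1 (Table 1) lists the number of participants with a meaningful score change under both secondary PRO objectives. SAP 5.8 fixes the time point: PROs are assessed by mean change "as well as by participants achieving of a meaningful score difference at the Cycle 13 visit". SAP 6.11.2.2 then calls for "The number and percentage of participants with a change representing a clinically meaningful improvement", with 95% Clopper-Pearson intervals, at an anchor-based and a distribution-based threshold. SAP 6.11.2.3.1 and 6.11.2.3.2 do the same for NRS-11 and PII with their own thresholds. None of these sections names a denominator.

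The general rules that fill the gap are these:

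- SAP 6.11: "The efficacy endpoints will include collected and derived continuous and categorical variables and will be summarized as described in" Section 5.1.2, unless otherwise specified.
- SAP 5.1.2, for categorical variables: "the absolute counts (n) and percentages (%) of participants in each with data". The same section sets a full-cohort denominator for adverse events, medical history and concomitant medications, but not for PRO improvement.
- SAP 5.5: "Missing data will only be imputed in the following cases". For these instruments the list covers averaging within a score and one imputation for dropout: "Monotone data, however, will be considered MNAR and imputed to be equal to the participant's baseline score". SAP 6.11.2.2 and 6.11.2.3 use that imputation only in the MMRM sensitivity analysis.
- SAP 6.11 also says: "The FAS will be the primary analysis set of interest in all efficacy analyses, unless otherwise specified".

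The primary endpoint, by contrast, has an explicit rule in SAP 4.1.1: "Participants who do not have a post-baseline MRI assessment or do not achieve a confirmed response will be categorized as non-responders".

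**The concern.** Read together, the default and the closed imputation list remove a participant with no Cycle 13 score from both numerator and denominator. In a single-arm trial no control group shares that selection. The reported rate and its exact interval then describe participants who stayed and completed the questionnaire, not those who were treated. If people who stop early for toxicity, progression or withdrawal improve less often, the rate overstates the benefit.

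No sensitivity analysis covers these proportions. The plan is cautious about missing data for the tumor endpoint and for the mean PRO changes, but silent for the improvement rates. The FAS statement in 6.11 pulls against the default in 5.1.2, so two programmers could defensibly report different percentages.

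**Working it through.** **1. Interval method.** The documents state no PRO improvement rate, so the nearest figures are those in SAP 2.3. Clopper-Pearson limits are the 0.025 quantile of Beta(x, n-x+1) and the 0.975 quantile of Beta(x+1, n-x).

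- 21/50: 28.2% to 56.8% (SAP: excludes 28%).
- 32/50: 49.2% to 77.1% (SAP: excludes 49%).

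Both reproduce. This checks the interval method at n = 50, nothing more.

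**2. Who has no Cycle 13 score.** SAP 5.6 (Table 13) maps non-nominal PRO records by study day; the Cycle 13 window is days 295 to 406.

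- Participants who leave after a scored Cycle 13 visit are kept.
- Those with a scorable PedsQL record in the window, including one from an early termination (ET) visit, are kept.
- For NRS-11 and PII, the ET visit collects one day only (SAP 4.1.2.2.2, 4.1.2.2.3). SAP 5.5.1.2 and 5.5.1.3 set the visit score to missing when at least 4 of 7 days are missing. One day leaves 7 - 1 = 6 missing, so an ET record alone gives no score, even inside the window. A safety follow-up diary week in the window could supply one.

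**3. Size.** Let N be the participants with a baseline score, m the fraction without a Cycle 13 score and x the number improved.

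- Observed-case rate: r = x / [N(1-m)].
- Missing counted as not improved: x / N = r(1-m).
- Ratio of the first to the second: 1/(1-m).

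The documents give no m. Assuming N = 50 (the planned cohort size; fewer children are eligible for NRS-11 and PII) and r = 40%:

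| m (assumed) | Observed case (95% CI) | Missing = not improved (95% CI) | Ratio | Gap (points) |
|---|---|---|---|---|
| 10% | 18/45 = 40.0% (25.7 to 55.7) | 18/50 = 36.0% (22.9 to 50.8) | 1.11 | 4 |
| 20% | 16/40 = 40.0% (24.9 to 56.7) | 16/50 = 32.0% (19.5 to 46.7) | 1.25 | 8 |
| 30% | 14/35 = 40.0% (23.9 to 57.9) | 14/50 = 28.0% (16.2 to 42.5) | 1.43 | 12 |
| 40% | 12/30 = 40.0% (22.7 to 59.4) | 12/50 = 24.0% (13.1 to 38.2) | 1.67 | 16 |

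**4. Direction.** If missing participants improve at rate q, the rate among all N is (1-m)r + mq, and the observed-case rate is off by r - [(1-m)r + mq] = m(r - q). At m = 20% and r = 40%:

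- q = 0 gives 32%, so the observed rate is 8 points high.
- q = 40% gives 40%, so there is no bias.
- q = 100% gives 52%, so the observed rate is 12 points low.

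**5. Responder versus non-responder comparison.** The first scheduled post-baseline MRI is Cycle 5, so the earliest scheduled confirmation is Cycle 9 Day 15: 8 × 28 + 15 = day 239. Participants who leave before a confirming scan are tumor non-responders under SAP 4.1.1. Assumed illustration: responders 15/25 improved; non-responders 6/15 improved, with 10 more missing.

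- Observed cases: 60% versus 40%. Pooled 21/40 = 0.525; SE = √[0.525 × 0.475 × (1/25 + 1/15)] = 0.163; z = 0.20/0.163 = 1.23; p about 0.22.
- Missing as not improved: 15/25 = 60% versus 6/25 = 24%. Pooled 21/50 = 0.42; SE = √[0.42 × 0.58 × (2/25)] = 0.140; z = 0.36/0.140 = 2.58; p about 0.01.

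The change comes entirely from the imputation.

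**The case against.** **The observed-case rule is not written in the PRO sections.** This stands. Elsewhere the SAP states a with-data denominator locally (for example 6.3, 6.4 and 6.9), and it does not do so here. The rule is inferred from 5.1.2. SAP 5.8 also assigns the methods and derivations of the meaningful-change analyses to an addendum that may set the denominator. However, the SAP calls itself complete and detailed in Section 1, Protocol 9.4 expects it to cover missing data, and the distribution-based PedsQL and PII thresholds and the fixed NRS-11 cut point are set in the SAP itself.

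**Naming the FAS settles it.** This does not stand. The FAS defines who belongs to the set, not how a missing score counts.

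**Missing data are already visible.** This partly stands. Numbers with a non-missing score are shown by visit, and completion rates use a fixed eligible-FAS denominator with reasons for missing data (SAP 6.10). A reader could approximate the alternative rate. Cycle 13 was also chosen partly to limit missing data. The headline percentage and its interval would still be the selected ones.

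**Table 1 lists a number, which no denominator alters.** This is true of the count, but the analysis sections report percentages with intervals. For PedsQL the distribution-based version is only supportive.

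**Stronger readings that the documents do not support.** A reader might infer that everyone who drops out leaves the rate, that the rate is therefore inflated, or that only the non-responder group loses participants. Later leavers and some in-window records are kept. The direction depends on how often missing participants improve. Confirmed responders can also leave between Cycles 9 and 13 or fall short of the diary minimum.

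**Conclusion.** The gap is real and should be closed. For the Cycle 13 improvement rates the SAP states no denominator, no rule for a missing score and no missing-data sensitivity analysis, and its default most naturally gives an observed-case rate. Relative to counting missing as not improved, that rate is higher by the factor 1/(1-m): 4 to 16 points over an assumed 10% to 40% missing when the observed rate is 40%.

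Calling this an overstatement of benefit among treated participants rests on one assumption: that those missing improve less often than those observed. The SAP adopts a similar view when it imputes no change after monotone dropout, but the documents give no dropout or PRO data to test it. The exposure is greater for NRS-11 and PII than for PedsQL, because an ET record alone cannot yield a pain score under the 7-day rule. The conclusion is subject to anything in the addendum.

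**What to change.** In SAP 6.11.2.2, 6.11.2.3.1 and 6.11.2.3.2, for the overall improvement rates in each cohort:

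- Set the denominator to FAS participants eligible for the instrument by age (Table 14) who have a baseline score.
- Count a missing Cycle 13 score as not improved. This matches the primary endpoint and the handling of dropout in 5.5.1.1. It is slightly broader than 5.5.1.1, which leaves intermittent gaps as missing at random.
- Show the observed-case rate and its interval as a supportive line.
- Align the addendum with this wording.

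Do not use this imputation as the main analysis in the tumor responder versus non-responder chi-square comparison. Early leavers are non-responders by definition, so coding them as not improved would build in an association. Keep that comparison on observed cases and report the number missing in each group.

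The cost is SAP wording and one denominator change, with no new data. The downside is a lower headline rate.
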